4.2 Study Objectives and Endpoints

The study objectives and endpoints to be evaluated in this study are presented in Table 1.

Table 1: Study Objectives and Endpoints

Objectives	Endpoints
Primary Objectives	Primary Endpoints
To compare the effects of graded exercise to passive stretching using ClearPlay© on symptomatic recovery rate following mTBI.	
 • Within-subject analysis of change in symptoms over time using the PCSS, comparing short-term ‘survival rates’ between graded exercise and stretching using Kaplan-Meier analyses for days since concussion.
Secondary Objectives	Secondary Endpoints
To compare the safety and tolerability of graded exercise to passive stretching in patients following mTBI.	
 • Adverse events reported from Day 1 through Day 56, including those identified during exercise or passive stretching during the 20 minutes of daily therapy.
To compare symptom resolution following graded exercise compared to passive stretching using ClearPlay© following mTBI.	
 • Within subject analysis of change in the number of subjects who are symptom free at 8 weeks between the 2 groups. Symptom free is defined by subjects having 3 consecutive days of PCSS scores lower than pre-concussion. 
Note: This objective is similar to the primary one, with the primary endpoint being recovery (binary outcome) vs. symptom resolution (continuous variable).
 
 • Determine differences in symptomatic recovery based on gender, baseline scores on the PCSS, baseline athletic fitness (Godin leisure-time exercise questionnaire), the history of injury, a history of migraine, as well as the presence of pre-morbid anxiety.
To compare the effects of graded exercise to passive stretching using ClearPlay© on physiologic recovery rate following mTBI.	
 • Within subject analysis of normalization of physiologic measurements obtained during the BCBT comparing data collected on entry to the study on Day 0 vs. follow up on Day 56 including: 
 - Beat to beat BP; • Determine differences in physiologic recovery based on gender, baseline scores on the PCSS, baseline athletic fitness (Godin leisure-time exercise questionnaire), the history of injury, a history of migraine, as well as the presence of pre-morbid anxiety (BAI; BSI-18; ASI).
To compare the effects of graded exercise to passive stretching using ClearPlay© on accelerating symptomatic vs. physiologic recovery rate following mTBI.	
 • Combined analysis of data from the two secondary analyses outlined above to confirm or refute a significant correlation between symptom resolution (defined by subjects having 3 consecutive days of PCSS scores lower than pre-concussion) and physiologic measurements obtained during the BCBT comparing data obtained on entry to the study on Day 0 vs. follow up on Day 56 including: 
 - Beat to beat BP;

Objectives	Endpoints
To develop a composite physiologic metric to predict the magnitude and duration of ongoing post-concussive symptoms.	
 • Develop predictive modeling algorithms to establish a composite physiologic metric predictive of subjects becoming symptom free (as defined by subjects having 3 consecutive days of PCSS scores lower than pre-concussion) using data derived from baseline physiologic testing with: 
 - BCBT - Ice bucket testing - ClearPlay© testing
To develop a composite neuropsychologic metric to predict the magnitude and duration of ongoing post-concussive symptoms.	
 • Develop predictive modeling algorithms to establish a composite neuropsychologic metric predictive of subjects becoming symptom free (as defined by subjects having 3 consecutive days of PCSS scores lower than pre-concussion) using data derived from baseline neuropsychologic testing with the following instruments: 
Attention (CAARS)
 
 - Depression (CES-D) - Anxiety (BAI; BSI-18; ASI).
To develop a composite blood-based or saliva biomarker metric to predict the magnitude and duration of ongoing post-concussive symptoms.	
 • Analysis of biomarkers at baseline testing including: 
 - Structural proteins [t-tau, NF-L, GFAP and UCH-L1] - Inflammatory cytokines [IL-6, IL-10 and TNFα] - SNPs [APO-E4, BDNF, and NFkB]
To validate the performance of ClearHeart© against ice bucket testing.	
 • Bland-Altman plots will be used to evaluate the agreement between HR measured by ClearHeart© and ice bucket testing. • Bland-Altman plots will be used to evaluate the agreement between BP measured by ClearHeart© and ice bucket testing.
To validate the performance of ClearNeck© against examination of the neck	
 • Correlations will be used to assess the association between results obtained through ClearNeck© testing and those obtained during the neurologic examination for neck range of motion and tenderness.

Abbreviations: ASI = Anxiety Sensitivity Index, BAI = Beck Anxiety Inventory, BCBT = Buffalo Concussion Bicycle Test, BESS = Balance Error Scoring System,; BP=blood pressure, BSI = Brief Symptom Inventory, CAARS = Conners' Adult Attention Deficit Hyperactivity Disorder Rating Scale, CES-D = Center for Epidemiologic Studies - Depression Scale,; HRV = heart rate variability; mTBI = mild traumatic brain injury; PCSS = Post-Concussive Symptom Scale, SNP = single nucleotide polymorphisms

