Analysis:	
No interim analysis is planned for this study.
 
In general, data will be summarized using descriptive statistics (number of non-missing observations, mean, median, standard deviation, minimum and maximum) or frequency counts and percentages, as appropriate to the type of data.
 
Adverse events and medical history will be coded with Medical Dictionary for Regulatory Activities (MedDRA, the latest version) and concomitant medications are coded with World Health Organization Drug coding Dictionary (latest version).
 
For all subjects, daily reported PCSS scores collected from ClearPlay© mobile application will be utilized to determine the resolution of symptoms. The resolution of symptoms is defined as a symptom-severity score of less than each subject's pre-injury PCSS score for 3 consecutive days. To assess differences in the probability of symptom resolution between graded exercise and passive stretching during the 8 weeks of therapy, both unadjusted and adjusted logistic regression models will be used. The primary outcome of the study will be to confirm or refute the superiority of sub-threshold aerobic exercise versus passive stretching to result in resolution of symptoms following mTBI. Confounders for the adjusted models will include age, gender, anxiety at baseline, history of migraine, cardiovascular fitness, the presence or absence of neurologic findings, and site of enrolment.
 
The survival probability will be compared using Kaplan-Meier (log rank test) analyses between the 2 treatment arms. Cox proportional hazards regression models will be used to evaluate the differences in time to symptom resolution. Adjusted treatment effects will be estimated in Cox proportional hazards regression models, controlling for the variables listed above. To identify that our randomization strategy was effective, analysis of variance will be used to assess for group-wise differences in age, days since injury to initial visit, initial PCSS score, resting heart rate (HR), and ΔHR during the BCBT and resting BP and ΔBP during the ice bucket test on Day 1. Non-parametric tests of medians will be used to compare the non-normally distributed variable duration of clinical recovery. Chi-

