9.6 Efficacy Analysis

The full presentation of the analysis of efficacy data will be presented in the SAP.

For all subjects, daily reported PCSS scores collected from ClearPlay© mobile application will be utilized to determine the resolution of symptoms. The resolution of symptoms is defined as a symptom-severity score of less than each subject's pre-injury PCSS score for 3 consecutive days. To assess differences in the probability of symptom resolution between graded exercise and passive stretching during the 8 weeks of therapy, both unadjusted and adjusted logistic regression models will be used. The primary outcome of the study will be to confirm or refute the superiority of sub-threshold aerobic exercise versus passive stretching to result in resolution of symptoms following mTBI. Confounders for the adjusted models will include age, gender, anxiety at baseline, history of migraine, cardiovascular fitness, the presence or absence of neurologic findings, and site of enrollment.

The survival probability will be compared using Kaplan-Meier (log rank test) analyses between the 2 treatment arms. Cox proportional hazards regression models will be used to evaluate the differences in time to symptom resolution. Adjusted treatment effects will be estimated in Cox proportional hazards regression models, controlling for the variables listed above. To identify that our randomization strategy was effective, analysis of variance will be used to assess for group-wise differences in age, days since injury to initial visit, initial PCSS score, resting HR, and Δ HR during the BCBT and resting BP and Δ BP during the ice bucket test on Day 1. Non-parametric tests of medians will be used to compare the non-normally distributed variable duration of clinical recovery. Chi-squared tests will be used to assess group-wise differences in gender, history of concussions, and incidence of PPCS.

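### The protocol does not settle its primary analysis: Table 1 makes a Kaplan-Meier comparison primary, while the sample size and the order of section 9.6 point to the proportion resolved by 8 weeks

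*Protocol*

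**What the plan says.** **Table 1 (section 4.2) and the Synopsis endpoint table.** The primary endpoint is a PCSS-based comparison of survival rates "between graded exercise and stretching using Kaplan-Meier analyses for days since concussion". A secondary endpoint is "Within subject analysis of change in the number of subjects who are symptom free at 8 weeks between the 2 groups". The note attached to that secondary endpoint describes the pair "with the primary endpoint being recovery (binary outcome) vs. symptom resolution (continuous variable").

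**Section 9.6 and the Synopsis analysis text.** The first analysis described is for a probability: "To assess differences in the probability of symptom resolution between graded exercise and passive stretching during the 8 weeks of therapy", for which "both unadjusted and adjusted logistic regression models will be used". The next sentence reads "The primary outcome of the study will be to confirm or refute the superiority of sub-threshold aerobic exercise versus passive stretching" and names no test. Two further analyses follow without ranking: "The survival probability will be compared using Kaplan-Meier (log rank test) analyses between the 2 treatment arms" and "Cox proportional hazards regression models will be used to evaluate the differences in time to symptom resolution".

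**Section 9.1.** The only effect size is 80% resolved on stretching against 93% on exercise. With 90% power and alpha 0.05 this gives 316, then 363 for 15% attrition, then 400 planned. There is no hazard ratio, event count or median.

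**Section 2.5.** The primary endpoint is resolution of self-reported symptoms, with no test named.

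**The concern.** The sections give incompatible accounts of what decides the trial. The endpoint table makes a time-to-event comparison primary. Its own note says the primary is binary and calls the secondary continuous, yet the secondary as listed is a count of symptom-free subjects. The note therefore fits neither row. The sample size and the order of section 9.6 point to the 8-week proportion, which the table lists as secondary. The Synopsis carries both versions.

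How fast subjects recover and how many have recovered by 8 weeks are separate questions. If the two tests disagree, one party could cite Table 1 for one result and another could cite 9.1 with 9.6 for the other. The trial is open label, sponsor included (6.3.1), and the SAP is due only before database lock (9.2). A choice left that late could be made with outcomes by arm already visible.

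**Working it through.** **1. Which test does 9.1 size?** Inputs from 9.1: p1 = 0.80, p2 = 0.93, power 90%, alpha 0.05, 1:1. Sidedness is not stated; two-sided is assumed.

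Wald test on the log odds ratio: n per arm = (1.960 + 1.282)² × [1/(p1q1) + 1/(p2q2)] / (ln OR)².
- OR = (0.93/0.07)/(0.80/0.20) = 3.32, so ln OR = 1.200.
- 1/0.16 + 1/0.0651 = 6.25 + 15.36 = 21.61.
- n = 10.507 × 21.61 / 1.441 = 157.6, so 158 per arm and **316 in total**, the stated figure.

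Other formulas give 318 (two proportions with continuity correction), 288 (pooled, uncorrected), 280 (unpooled) and 274 (arcsine). One-sided versions give 264 or fewer. Whichever was used, 9.1 is a calculation for a proportion.

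**2. What a log-rank primary would need.** Assuming proportional hazards and reading 80% and 93% as Day-56 rates:
- HR = ln(0.07)/ln(0.20) = 1.652.
- Events (Schoenfeld) = 4 × 10.507/(ln 1.652)² = 167.
- The average resolved is (0.80 + 0.93)/2 = 0.865, so 167/0.865 gives 194 evaluable subjects.

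At 340 evaluable (400 × 0.85; 294 events) formula power is 99.1% for log-rank, 94.3% for the pooled two-proportion test and 92.0% for the log-odds-ratio Wald test.

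**3. How often the verdicts differ.** Simulation with 170 per arm, two-sided 0.05, daily scores and exponential times (assumed); 10,000 runs per row.

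| Resolved by Day 56 | Log-rank rejects | Proportion test rejects | Verdicts differ |
|---|---|---|---|
| 80% vs 93% (plan) | 99.0% | 95.0–95.3% | 4.0–4.4% |
| 80% vs 88% (assumed) | 64.5% | 52.2–53.3% | 18.0–18.5% |

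The ranges cover the logistic Wald and two-proportion tests.

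Speed-only effect: 86.5% resolve by Day 56 in both arms but exercise gets there sooner. Over ten assumed patterns (4,000 runs each), log-rank rejects in 21–59% of trials and the proportion test in 4–6%. Only the direction is robust.

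No effect (80%, 86.5% or 93% in both arms): each test alone rejects in about 5%. If either could support the claim, the rate is 7–8%. The protocol states no such rule, so this is what the ambiguity would permit and not a property of the plan.

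**4. Time origin.** Section 9.6 gives none. Table 1 counts from concussion, which adds 3 to 14 days before Day 0 in which no event can be counted. With entry uniform on days 3–14 (assumed; 6,000 runs) at 80% versus 93%, log-rank power is 99.0% from randomisation and 98.9% from concussion, and verdicts differ in 0.3% of trials. Only the medians move: 24.2 and 14.7 days (stretching, exercise) from randomisation against 32.9 and 23.4 from concussion.

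**5. Attrition.** 316 × 1.15 = 363.4, the stated 363. But 363 × 0.85 = 308.6, below 316. Retaining 316 after a 15% loss needs 316/0.85 = 371.8, so 372. The planned 400 leaves 400 × 0.85 = 340.

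**The case against.** The best counter-argument is that 9.6 never labels the logistic models primary. Its primary-outcome sentence names no test and is compatible with log-rank, and the one place that ties a method to the word primary is Table 1. The stated aim of accelerating recovery (2.5) points the same way, and 9.6 defers full presentation to the SAP. On this reading 9.6 is unranked, not contradictory. That is fair for 9.6 alone. It does not remove the conflict between Table 1 and its own note, nor explain why 9.1 powers only the endpoint that Table 1 makes secondary. The SAP cannot resolve this either: under 9.2 it carries out the protocol's principal features, and those conflict.

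Matching 316 to a logistic test is inference, since 318 from another formula is close. The formula is also conservative: exact enumeration puts the Wald test at about 93% power with 158 per arm. What stands is that 9.1 sizes a proportion; the exact formula is not essential.

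At the plan's own effect the verdicts rarely differ, and the larger figures rest on assumed scenarios. That is correct. In addition, 9.8 keeps withdrawals in the analysis up to withdrawal, so log-rank would use all 400 with censoring. With 15% uniform dropout (assumed) its power is about 99.9% and 68% in the two table rows, not 99% and 64%. This changes the size of the gap between the tests, not the need to choose one.

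**Conclusion.** Wrong as written, and it must be fixed. The protocol supports two different deciding analyses, and its own note contradicts the table it annotates. That rests on the text alone. The size depends on the truth: about 4% of trials with conflicting verdicts at 80% versus 93%, 18–19% at 80% versus 88%, and more if exercise mainly speeds recovery. These figures assume 340 evaluable subjects, exponential times and, for the speed-only cases, invented patterns. Power is adequate for either analysis at the planned effect, so this is not a sample-size problem. The missing time origin and the 363 are minor: the first hardly affects the test, and the second does not change enrolment.

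**What to change.** Name one primary endpoint and one test, in the same words, in the Synopsis (endpoint table and analysis text), 2.5, Table 1, 9.1 and 9.6. Make the other analyses secondary.

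- **Option (a): resolution within 8 weeks**, with one named test. The unadjusted logistic model fits 9.1 as it stands. If the adjusted model is chosen, 9.1 should say that its two marginal proportions only approximate it. Because 9.8 excludes imputation by default, also state how subjects withdrawn before resolving are counted. Kaplan-Meier and log-rank become secondary.
- **Option (b): time to resolution by log-rank**, preferably stratified by the randomisation factors (site and baseline PCSS below versus at or above 30). Restate 9.1 for that test and say that it assumes proportional hazards.

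Under either option, delete or correct the binary/continuous note in both Table 1 and the Synopsis. Give the time origin for log-rank and Cox in 9.6; randomisation is the cleaner choice. Change 363 to 372 in 9.1.

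The cost is protocol wording, with the same data collection and the same 400 subjects. One of the two analyses loses primary status, and option (b) needs a new power statement.

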4 STUDY DESIGN AND ENDPOINTS

4.1 Description of the Study Design

This study is designed as an open label study of a therapeutic intervention in subjects who have sustained mTBI. At least 400 subjects aged 14 to 45 inclusive will be enrolled in this study at up to 5 study sites. Subjects will be randomly assigned with a ratio of 1:1 to complete either graded exercise or passive stretching. The study sites will have well-established concussion research programs and referral populations.

The therapeutic intervention is either 20 minutes daily of graded exercise or 20 minutes daily of passive stretching delivered through the ClearPlay© mobile application, downloaded to an Apple i-touch or i-phone device, used in conjunction with a wrist-worn heart rate monitoring device (Waveband®). The sponsor will provide one i-touch or i-phone to each subject to provide them with access to ClearPlay App. This device will also allow subjects to access music for use during exercise or stretching.

Randomization of each subject will occur when the subject has completed all of their Baseline physiologic testing (Ice Bucket Test, ClearHeart© and BCBT) on Day 0.

[figure not shown]
Both the site staff treating subjects and the subjects themselves will be aware of the assigned exercise regimen. Subjects will be stratified based on baseline scores on the PCSS (threshold ≥ 30).

The study consists of 2 study visits and 3 remote telephone visits between the 2 study visits:

- Study Visit 1 (Day 0) – Screening/Baseline visit: within 3 to 14 days of concussion. This visit will serve as a screening visit, to determine eligibility to participate in the study. Eligible subjects will be enrolled, and baseline assessments performed;
- Remote telephone safety assessments – Day 14, Day 28 and Day 42 for safety follow up;
- Study Visit 2 – Follow-up visit: 8 weeks following enrolment (Day 56).

A schematic diagram of the study design is presented in Figure 2.

Figure 2: Study Design

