5 STUDY ENROLMENT AND WITHDRAWAL

5.1 Inclusion Criteria

To be eligible for study entry subjects must satisfy all of the following criteria:

1. Male or female subjects aged ≥ 14 to ≤ 45 , able and willing to provide informed consent (≥ 18 years), or informed consent is obtained by the parent or legal guardian for minor subjects, with the minor providing age appropriate assent, according to local law and regulations;

2. Subject is fluent in English, able to understand and agree to comply with protocol requirements, and complete all assessments;
3. Subject has a history of recent concussion as diagnosed by a health care professional within 3 to 14 days of enrolment;

Note: Concussion is defined as a head injury/blow to the head resulting in any of the following 3 signs and/or new symptoms: (1) amnesia for less than 24 hours; (2) Loss of consciousness for less than 30 minutes; (3) Glasgow Coma Scale score ≥ 13 ; (4) Dazed and Confused/bell rung; with at least 1 new symptom or augmentation of a previous symptom on the PCSS as compared with baseline at the time of enrolment, including: headaches, dizziness, fatigue, irritability, insomnia, difficulty concentrating, and/or memory difficulties; (5) The composite symptom score on the PCSS must be at least 3 points higher post-concussion than pre-concussion.

4. Subject has daily access to the internet.

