6.3.2 Randomization

A computer-generated randomization schedule will be prepared by a statistician prior to the start of the study. Treatment allocation will be made per the randomization list.

After signing the informed consent form/providing assent, subjects will be administered the screening instruments via REDCap Cloud, along with generation of unique subject ID.

Once eligibility has been established, subjects must proceed to complete all Baseline assessments. The Order of Assessment is listed in Section 8.1, Table 4. Randomization of each subject will occur when the subject has completed all of their Baseline physiologic testing on Day 0.

The subject will be assigned a unique randomization number, which will be allocated sequentially based on the pre-determined randomization schedule, and according to their chronological order of inclusion in the study.

Both the unique subject ID and randomization numbers will be used to identify the subject throughout the study period and on all study-related documentation.

Stratification: randomization will be stratified at each enrolment site by the baseline symptom severity score on the PCSS (threshold $<$ or ≥ 30). The baseline PCSS score is reflective of multiple pre-morbid, neurologic, psychologic, and other factors that collectively are likely to significantly impact the presence of PCSS. Rather than stratify the population based on

individual factors, the single composite measure should provide the most efficient and effective starting point for this clinical trial.

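### The primary Kaplan-Meier clock starts at concussion, 3 to 14 days before randomisation, so unless delayed entry is used the curves and medians include event-free time and do not match the 8-week therapy window

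*Protocol*

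**What the plan says.** The primary endpoint in Protocol section 4.2 (Table 1), repeated in the synopsis, compares the arms "using Kaplan-Meier analyses for days since concussion".

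The design starts later than that clock. Section 4.1 describes Day 0 as "Screening/Baseline visit: within 3 to 14 days of concussion", and section 5.1 sets the same interval as an entry criterion. Section 6.3.2 places the treatment assignment on Day 0: "Randomization of each subject will occur when the subject has completed all of their Baseline physiologic testing". Entrants must not have recovered: "The composite symptom score on the PCSS must be at least 3 points higher post-concussion than pre-concussion".

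The event comes from one source. Section 9.6 states that "daily reported PCSS scores collected from ClearPlay© mobile application will be utilized to determine the resolution of symptoms" and defines resolution as a "symptom-severity score of less than each subject's pre-injury PCSS score for 3 consecutive days". In Table 4 (section 8.1) the device carrying the app is dispensed after randomisation. The follow-up visit in section 4.1 is 8 weeks after enrolment, at Day 56.

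For the logistic models, section 9.6 names a different window: "To assess differences in the probability of symptom resolution between graded exercise and passive stretching during the 8 weeks of therapy". For the log-rank and Cox analyses it names no time origin. Delayed entry is not mentioned anywhere in the protocol.

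**The concern.** A Kaplan-Meier curve treats a subject as at risk from time zero unless told otherwise. Here time zero is the injury, but nobody can have a recorded event until they have been randomised and given the app. Each subject therefore brings 3 to 14 days in which the event was impossible. If resolution is dated to the third qualifying day, the earliest possible event is about day 6 after concussion for someone entering on day 3, and about day 17 for someone entering on day 14.

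Three things follow if the wording is applied as it stands:

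- The curves are held up at the start and shifted to the right by an amount that depends on how quickly sites enrolled.
- Any day t on the curve mixes subjects who have had between t − 14 and t − 3 days of therapy.
- Day 56 of the study falls between day 59 (3 + 56) and day 70 (14 + 56) on this clock, so the primary curves and the logistic analysis describe different windows.

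At stake are the descriptive results of an endpoint about recovery rate: the curves, the medians and the percentage recovered by a given day.

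**Working it through.** **The plan's own figure.** Section 9.1 gives 316 subjects for 80% vs 93%, 90% power and α = 0.05. A two-sided comparison of two proportions with continuity correction gives 159 per arm, 318 in total, which is close to 316. The calculation compares proportions, so the time origin does not enter it.

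**Inputs.** From the protocol: resolution probabilities of 80% (stretching) and 93% (exercise), entry 3 to 14 days after injury, and follow-up of 56 days from enrolment. Assumed for illustration: the 80% and 93% refer to 56 days of therapy, recovery from randomisation is exponential, entry is uniform on the whole days 3 to 14, and there is no dropout.

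**Bound that needs no shape assumption.** Let T be days from randomisation to resolution and d the entry delay. Since 3 ≤ d ≤ 14, the unresolved proportion on the concussion clock at day t lies between the randomisation-clock value at t − 3 and that at t − 14. With complete follow-up, each median moves 3 to 14 days later.

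**Rates.** λ = −ln(unresolved at 56)/56.
- Stretching: −ln(0.20)/56 = 0.02874 per day.
- Exercise: −ln(0.07)/56 = 0.04749 per day.
- Hazard ratio: 0.04749/0.02874 = 1.65.

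**Unresolved at day 56 of the concussion clock.** For t ≥ 14, S(t) = exp(−λt) × M, where M is the mean of exp(λd) over d = 3, …, 14.
- Stretching: M = 1.283, so 0.20 × 1.283 = 25.7%.
- Exercise: M = 1.517, so 0.07 × 1.517 = 10.6%.

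**Medians.** From randomisation the median is ln 2/λ. From concussion it is (ln 2 + ln M)/λ.
- Stretching: 0.693/0.02874 = 24.1 days; (0.693 + 0.249)/0.02874 = 32.8 days.
- Exercise: 0.693/0.04749 = 14.6 days; (0.693 + 0.417)/0.04749 = 23.4 days.

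| Stretching / exercise | From randomisation | From concussion, no delayed entry |
|---|---|---|
| Resolved by day 28 | 55% / 74% | 43% / 60% |
| Unresolved at day 56 | 20% / 7% | 25.7% / 10.6% |
| Median, days | 24.1 / 14.6 | 32.8 / 23.4 |
| Difference in medians, days | 9.5 | 9.4 |

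**Range over entry delay.** S(56) = exp(−λ(56 − d)). If all enter on day 3, 21.8% vs 8.1% are unresolved; if all enter on day 14, 29.9% vs 13.6%.

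**Effect on the comparison.** A simulation with 158 per arm, under the same assumptions and with recovery counted in whole days, gave:

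| | From randomisation | From concussion, no delayed entry | From concussion, delayed entry |
|---|---|---|---|
| Cox hazard ratio | 1.642 | 1.636 | 1.641 |
| Log-rank power | 98.3% | 98.3% | 98.3% |
| Rejection rate, 80% in both arms | 5.5% | 5.4% | 5.5% |

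**The case against.** Time since injury is a sensible scale for this condition. The objective is recovery after mTBI, section 2.1 defines persistent symptoms by their total duration, and section 9.6 compares their incidence. Total symptom duration among enrolled subjects is a coherent quantity. That stands, and it is a reason to keep a since-concussion curve as a supplement. It does not make that curve a description of recovery during therapy.

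The protocol also does not say how risk sets are formed, and it leaves the full efficacy presentation to the SAP, which is not at hand. A concussion clock with entry at randomisation would fit Table 1 and would remove the guaranteed event-free time. That stands too, so the point is conditional on delayed entry not being used. The mismatch between the clock in Table 1 and the therapy window in section 9.6 is in the protocol itself and would remain.

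Three stronger readings are tempting, and the document does not support them:

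- A reader might infer that the treatment test is biased. Randomisation balances the delay, and the hazard ratio, power and type I error are practically the same on either clock.
- A reader might infer that the trial's results could not be set against the 80% and 93% used for sizing. The logistic models estimate the probability of resolution over the 8 weeks of therapy, and they do not depend on the Kaplan-Meier clock.
- A reader might infer that the distorted medians are the trial's headline estimates. The protocol does not name Kaplan-Meier medians or day-56 probabilities as the primary estimate; it uses the method to compare the arms.

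The ratio of medians does fall, from 24.1/14.6 = 1.65 to 32.8/23.4 = 1.40, but only because a common lag is added to both. The absolute difference stays at about 9.5 days.

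**Conclusion.** The point holds as a matter of description and consistency. With the clock in Table 1 and no delayed entry, the primary curves carry 3 to 14 event-free days per subject. They understate recovery after the same number of days of therapy: at day 56 by 5.7 points for stretching and 3.6 for exercise, and at day 28 by about 13 and 14 points. Both medians come out about 9 days later.

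These sizes rest on exponential recovery, uniform entry, no dropout, and 80% and 93% being reached at 56 days of therapy. The 3-to-14-day limits on the shift rest only on the protocol's entry window and complete follow-up. The between-arm comparison and the logistic analysis are sound on this point. It is worth correcting because it sits in the wording of the primary endpoint and leaves its curves on a different window from the binary analysis of the same event.

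**What to change.** In Table 1, the synopsis and section 9.6, state one time origin for the Kaplan-Meier, log-rank and Cox analyses: randomisation (Day 0), with censoring at Day 56.

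Add days from injury to randomisation to the Cox covariates. Section 9.6 already uses days from injury to the initial visit as a balance variable, and that visit is Day 0, so the value is collected; it is only absent from the adjustment list. Balance between arms does not depend on this, but if delay predicts recovery, adjusting for it avoids a hazard ratio pulled towards 1.

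If total symptom duration is of interest, show a since-concussion curve as a supplement, with each subject entering the risk set at randomisation.

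The cost is a change of wording. No new data, visits or subjects are needed.
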